6.1.1 Blinding the Treatment Assignment

6.1.2 Double-Blind Phase

During the double-blind phase of the study, all participating staff involved in the evaluation and execution of the study will remain blinded to the participant's treatment assignment.

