6.2.4 Investigational Product Infusion Precautions

Throughout the study, heart rate and rhythm, blood pressure, and oxygen saturation are monitored. Investigational product may be temporarily or permanently discontinued, if clinically indicated, for treatment of persistent hypotension (sustained systolic blood pressure <90 mmHg), cardiac arrhythmia or oxygen desaturation.

Due to Captisol® presence in the IV formulation of the IP, renal function will be monitored throughout the study. In addition to standard and accepted biomarkers of renal function (i.e., creatinine clearance and estimated glomerular filtration ratio [eGFR]), urinary exploratory biomarkers of renal function (N-acetyl-β-D-glucosaminidase [NAG], β2-microglobulin, and creatinine) will be monitored throughout the study and reviewed by the DMC.

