8.1.5 Clinical Laboratory and Other Safety Evaluations

A change in the value of a clinical laboratory, vital sign, or ECG assessment can represent an AE if the change is clinically significant or if, during treatment with the IP, a shift of a parameter is observed from a normal value to an abnormal value, or there is a further worsening of an already abnormal value. When evaluating such changes, the extent of deviation from the reference range, the duration until return to the reference range (either while continuing treatment or following IP discontinuation), and the range of variation of the respective parameter within its reference range must be taken into consideration.

At the end of the treatment phase, for participants who complete the study and do not progress to an IV anesthetic for seizure suppression, if there are abnormal clinical laboratory, vital sign, or ECG values that were not present in the pretreatment assessments closest to the start of IP initiation, further investigations should be performed until the values return to within the reference range or until a plausible explanation (e.g., concomitant disease) is found for the abnormal values.

The investigator should decide, based on the above criteria and the clinical condition of a participant, whether a change in a clinical laboratory, vital sign, or ECG parameter is clinically significant and therefore represents an AE.

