2. STATISTICAL CONSIDERATIONS

2.1 General Considerations

- The treatment groups will be coded as “Ganaxolone” and “Placebo,” and all summary tables will be provided by treatment group and overall. When applicable, treatment in open-label phase will be coded as “Openlabel Ganaxolone”.
- In general, descriptive statistics (n, mean standard deviation [SD], median, 25th and 75th percentiles, minimum, and maximum) will be summarized by treatment group for continuous variables. Means and medians will be presented with one more decimal place than the precision of the data. Standard deviations will be presented with two more decimal

places than the precision of the data. Minimums and maximums will be presented with the same precision as the original data.

- Count and percentage of participants in each category will be provided for categorical variables. Unless stated otherwise, percentages are based on the number of participants in the treatment group of the analysis set. Percentages will be presented with one decimal place (xx.x), with the exception of 100%, which will be displayed without any decimal places, and the exception of 0%, which will not be displayed.
- All listings will be listed by treatment group, participant, test parameter, and time point (if applicable).
- Scheduled assessments will be included in summaries. Unscheduled assessments will only be included in the display sections that report abnormal laboratory results, vital signs, or ECG values. Data from all assessments (scheduled or unscheduled), will be included in the listings.
- Unless stated otherwise, baseline is defined as the last non-missing value prior to the first dose of study drug administration.
- P-values will be reported to 3 decimal places, with values less than 0.001 displayed as “<0.001.”
- All outputs should have the following header at the upper left margin:

Marinus Pharmaceuticals, Inc.
Study 1042-SE-3003

And the following header (right justified) at the upper right margin:

Page n of N

Tables/appendices/listing should be internally paginated (i.e., page numbers should appear sequentially within each table). All outputs should have SAS program name, source listing, and execution date and time included in the footnotes.

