2.3 Time Windows for Analyses

For by-visit safety or efficacy summaries, only scheduled visits will be analyzed. Data collected at unscheduled visits will be provided in listings.

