3.3.3 Laboratory Evaluations

All laboratory parameters will be presented in Standard International (SI) units. Only scheduled lab parameters will be included in the lab summaries.

Laboratory data collected in this study include serum chemistry and hematology values, urinalysis results, pregnancy results, and drug of abuse results. The baseline laboratory value is defined as the last value observed prior to IP initiation. Any values collected after IP initiation are regarded as post-baseline. Change from baseline will be calculated as the post-baseline value minus the baseline value. Only the numeric part in laboratory values that contain non-numeric qualifiers, such as less than (<) a certain value or greater than (>) a certain value, will be used in the summary statistics.

Quantitative results (including actual value and change from baseline) will be summarized using descriptive statistics by baseline and post-baseline visit for each laboratory test based on the Safety Population. Shift tables cross-tabulating the baseline and post-baseline classifications (below [L], Normal [N], or above [H] the reference range), by visit, will be provided.

All laboratory data will be included in the listing, including whether the value was below (L), within (N), or above (H) the normal reference range (some urinalysis labs are assigned only normal and abnormal classifications).

Pregnancy results performed on selected participants will be listed.

Screening results for drugs of abuse, including alcohol, will be listed separately.

All blood gas results, including FiO₂, PaO₂, and arterial pH, if available will be listed.

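### SAP 3.3.3 gives no by-arm count of participants with a given creatinine rise; its scheduled-only, by-visit displays show only part of a renal signal

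*SAP*

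**What the plan says.** Protocol 6.2.4 gives the reason for renal attention: "Due to Captisol® presence in the IV formulation of the IP, renal function will be monitored throughout the study". The same section says that urinary renal biomarkers are followed and reviewed by the DMC.

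SAP 3.3.3 treats all laboratory tests alike:

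- by-visit descriptive statistics of the value and of the change from baseline;
- three-class shifts: "Shift tables cross-tabulating the baseline and post-baseline classifications (below [L], Normal [N], or above [H] the reference range), by visit, will be provided";
- a listing of all values with a low, normal or high flag.

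SAP 2.1 splits all summary tables by treatment group, so these displays are by arm.

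Two rules restrict the input: "Only scheduled lab parameters will be included in the lab summaries" (SAP 3.3.3) and "For by-visit safety or efficacy summaries, only scheduled visits will be analyzed" (SAP 2.3). SAP 2.1 allows an exception: "Unscheduled assessments will only be included in the display sections that report abnormal laboratory results, vital signs, or ECG values". SAP 3.3.3 defines no such display. Footnote i of Protocol Table 1 calls for chemistry when an SAE occurs, which is outside the visit schedule.

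The only renal cut-offs found are exclusion criterion 9 (known or suspected stage 3B or worse, eGFR 44 or lower) and the example of eGFR 44 or lower among the reasons to discontinue in Protocol 4.5.2. Neither is an analysis category.

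**The concern.** A safety reader will want to know how many participants in each arm had a substantial rise in creatinine. The specified displays do not answer that, for three reasons.

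1. A participant who starts above range stays in the high-to-high cell however far creatinine rises. Exclusion criterion 9 limits such baselines but does not remove them.
2. By-visit tables do not follow the participant. One rise at each of four visits may be four people or one.
3. Samples drawn because a participant had an SAE, often the ones of most interest, do not enter the 3.3.3 summaries.

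At stake is the clarity of the renal read-out for a product given close to its stated limit. For participants of 40 kg or more, the Day 1 dose is 30 + 80×2 + 40×10 + 20×12 = 830 mg, against a cap of 833 mg that corresponds to 50 g of Captisol. If no threshold table is fixed in advance, any later count would use cut-offs chosen after unblinding.

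**Working it through.** The plan states no figure on this point, so there is none to reproduce. The check asks whether the specified displays determine the count of affected participants.

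**Shift classes.** Assume a reference range of 50–110 µmol/L.

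| Baseline → later | Ratio | Shift cell |
|---|---|---|
| 115 → 115 | 1.0 | H to H |
| 115 → 230 | 2.0 | H to H |
| 115 → 345 | 3.0 | H to H |
| 70 → 105 | 1.5 | N to N |
| 105 → 115.5 | 1.1 | N to H |
| 70 → 210 | 3.0 | N to H |

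No change and a threefold rise share a cell when the baseline is high. A 1.1-fold and a threefold rise share a cell when the baseline is normal.

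**By-visit statistics.** Assumed inputs: 50 per arm (about 100 were randomised 1:1) and four scheduled post-IP chemistry visits (IP discontinuation, 24 hours later, discharge, one weekly visit). In each arm, 4 participants have a baseline of 133 µmol/L and 46 have 80. The reference range contains 80 and its upper limit is below 133.

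- Arm A: each of the four is at 266 at one visit, a different visit for each.
- Arm B: one of the four is at 266 at all four visits.

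At every visit, in both arms:

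- mean value = (266 + 3×133 + 46×80)/50 = 4345/50 = 86.9; SD 28.8; median and quartiles 80; maximum 266;
- mean change = 133/50 = 2.66; SD 18.8; median and quartiles 0; maximum 133;
- shifts: 4 H to H, 46 N to N.

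The planned summaries are the same. Participants who ever at least doubled (Clopper-Pearson 95% intervals):

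- arm A: 4/50 = 8% (2.2% to 19.2%);
- arm B: 1/50 = 2% (0.05% to 10.65%).

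In general, c participants above a cut-off at each of V visits is compatible with c to V×c participants ever above it. With c = 1 and V = 4, that is 1 to 4.

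**Clustered rises.** If all four in arm A rise at the same visit, the mean change there is 4×133/50 = 10.64 against 2.66, and the SD is 36.4 against 18.8. The arms then separate, but the number of participants is still not reported.

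**SAE-triggered values.** Suppose one more arm A participant, with baseline 80, reaches 160 or more only in a sample drawn for an SAE. The count is 5/50 = 10% (3.3% to 21.8%) with all values and 4/50 with scheduled values only. The 3.3.3 summaries do not change.

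**The AE route.** Let investigators record such a rise as an AE with an assumed probability p of 0.5 to 1.0. For the 4 against 1 case, the TEAE table shows on average 4p = 2 to 4 participants in arm A and p = 0.5 to 1 in arm B.

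**The case against.** The strongest reply is that this asks for one more table and that no promised analysis is missing. Protocol 10.5 requires only that laboratory tests be summarised by treatment group, and SAP 3.3.3 does that. Other parts of the plan also carry renal information:

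- TEAE tables are by arm and count each participant once per event. Protocol 8.1.5 names as a ground for an AE that "there is a further worsening of an already abnormal value".
- Maximum change by visit shows the largest single rise, and BUN (with eGFR and creatinine clearance where available) appears in the same form.
- The DMC reviews urinary renal biomarkers, and the eGFR example in Protocol 4.5.2 can lead to discontinuation, whose reasons are summarised.
- All values are listed, so the count can be reconstructed.

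Most of this stands, and it limits the weight of the point. What it does not supply is an objective count. Under Protocol 8.1.5 the investigator decides "whether a change in a clinical laboratory, vital sign, or ECG parameter is clinically significant and therefore represents an AE", without a fixed threshold. Because "all participating staff involved in the evaluation and execution of the study will remain blinded", under-recording need not favour either arm, but it still lowers the number seen. A count rebuilt from listings would use cut-offs that were not fixed beforehand.

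The identical-arms example is contrived: it needs four different peak visits and exact returns to baseline. It proves only that the summaries do not determine the count. It does not predict a result.

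A further objection is right and shapes the fix. A highest-ever value over four weeks depends on how often a participant is sampled, and weekly draws depend on whether the participant is still in hospital.

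The table templates are filed separately (SAP 6) and were not seen. A suitable display may exist there.

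**Conclusion.** The point holds as a cheap improvement that should be made. As written, SAP 3.3.3 cannot show creatinine worsening from an above-range baseline, does not report how many participants ever had a given rise, and leaves SAE-triggered values to the listings. In the illustration this hides a difference of 4 against 1 participants in 50. All creatinine values there are assumed, and the intervals overlap.

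Three stronger readings are tempting and not supported:

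- That renal harm would go unseen. The TEAE tables, maximum change, listings, DMC review and discontinuation data would each show part of it.
- That the SAP contradicts the protocol or misstates a result. The protocol promises no threshold table. The exception in SAP 2.1 for abnormal-result displays sits awkwardly with 3.3.3, but that is a loose end and not an error in a figure.
- That a by-arm difference would measure the effect of Captisol. Protocol 6.1 describes the composition of the active formulation only, and the documents do not say whether placebo contains Captisol. The contrast concerns the IP as given.

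Confidence is medium, mainly because the templates were not available.

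**What to change.** Add one descriptive table to SAP 3.3.3, by arm in the Safety Population, with no test: the number and percentage of participants whose highest post-IP serum creatinine, scheduled or unscheduled, is at least 1.5, 2 and 3 times the pre-IP baseline. These cut-offs are a reviewer's choice and appear in neither document.

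- **Main window:** a fixed period from IP initiation, for example 96 hours. With a full 48-hour infusion, the sample 24 hours after discontinuation falls at 48 + 24 = 72 hours, so the window holds the two scheduled post-IP samples before discharge. Participants who stop early have these samples sooner, still inside it.
- **Supplement:** the full follow-up, labelled as dependent on length of stay.
- **Repeat:** scheduled values only, because SAE-triggered sampling may differ by arm.
- **Denominator:** participants with a pre-IP value and at least one post-IP value in the window. Report the number without a pre-IP value, because footnote i of Protocol Table 1 lets the screening sample be drawn up to 2 hours after IP initiation.
- **Note to the table:** the contrast concerns the IP as given.

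Cost: SAP wording and one more table from data already collected, with no effect on alpha or the efficacy analyses. Participants without a pre-IP value drop out of the ratio; they have no baseline for the planned change and shift tables either.

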3.3.4 Electrocardiogram

Descriptive statistics for ECG parameters (PR interval, RR interval, QRS interval, QT interval, QTcF [QT interval corrected using Fridericia's method], QTcB [QT interval corrected using Bazett's method], heart rate) and changes from baseline values at each time point will be provided.

In addition, the number and percentage of participants in each category of the interpretation (normal, abnormal not clinically significant, abnormal clinically significant) will be summarized.

Select sites will participate in a substudy using a continuous 12 lead ECG recorder which should start approximately 60 minutes prior to IP initiation and should continue for 36 hours following IP initiation. The data from the substudy of cardiodynamic 12 Lead Electrographic (ECG) monitoring will be summarized in separate tables using the same approach as for the main study if the data is ready by the primary analysis.

All ECG data will be presented in the data listing.

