APPENDIX 5 CARDIODYNAMIC 12 LEAD ELECTROGRAPHIC (ECG) MONITORING

Select sites will participate in a sub study using a continuous 12 lead ECG recorder which should start approximately 60 minutes prior to IP initiation and should continue for 36 hours following IP initiation.

Periods/Day/ Duration	Screening Day -1 to Day 1 Predose through screening	Dosing Day 1 IP initiation 0 through 24 hours following IP initiation	Dosing Day 2 24 hours through 36 hours following IP initiation	Taper Day 2 (12 hours) Starts at 36 hours following IP initiation
IP infusion		✓	✓	✓
Timepoint	-60 minutes	0 through 24 hours following IP initiation	24 hours through 36 hours following IP initiation	36-48 hours following IP initiation
Cardiodynamic 12 lead ECG monitoring	✓	✓	✓	✓

Replicate ECGs will be extracted from the recorder devices by the ECG vendor at 3 timepoints prior to IP initiation (-45, -30 and -15 minutes) at least 1 minute apart within + 3 minutes window. Post dose replicate ECGs will be extracted by the ECG vendor at timepoints that match the PK collection times. Whenever the ECG extraction and PK or clinical safety lab sample collection timepoints are close together, the ECG extraction will be performed prior to the PK or clinical safety lab sample collection.

Reference the Cardiodynamic ECG Manual for further details.

APPENDIX 6 SUMMARY OF CHANGES FROM PROTOCOL AMENDMENT 1

Protocol Amendments		
Summary of Change(s) Since Last Version of Approved Protocol		
Amendment Number	Amendment Date	Global/Country/Site Specific
1		Global
Description of Change		Section(s) Affected by Change
Added [name], as the back-up emergency contact		Emergency Contact Information
Clarified that the administration of an anesthetic for seizure suppression should be given at an adequate dose and for an adequate duration to induce anesthesia		Synopsis; Section 6.2.6
Revised the sentence regarding the central reader to include 'confirmatory' analysis and that the central reader is blinded to treatment assignment		Synopsis, Section 6.2.3
Removed 'and neurological' from physical examination as the neurological assessment is included in the physical examination		Synopsis, Table 1, Section 7.2.3.2
Added the following timepoints to the Richmond Agitation and Sedation Scale (RASS) and the Full Outline of UnResponsiveness (FOUR) Score Scale: 60 minutes (+/- 15 min), 2, 6 hours (+/- 30 min), and 36 hours (+/- 1 hour)		Synopsis, Table 1

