3.3 Safety Analysis

All the safety summaries are based on the Safety Population. Baseline is defined as the last non-missing value prior to the first dose of study drug administration.

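### The cardiodynamic ECG substudy collects three predose timepoints, but the SAP's rule uses only the last as baseline and plans no ganaxolone-minus-placebo QTcF difference or interval

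*SAP*

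**What the plan says.** Protocol Appendix 5 describes continuous 12-lead recording at selected sites, from about 60 minutes before dosing to 36 hours after. The vendor extracts replicate ECGs "at 3 timepoints prior to IP initiation (-45, -30 and -15 minutes" before dosing. For the period after dosing, "Post dose replicate ECGs will be extracted by the ECG vendor at timepoints that match the PK collection times"; within the 36-hour recording those are 60 minutes and 2, 6, 10, 24 and 36 hours (Protocol Table 2). The appendix refers to a Cardiodynamic ECG Manual for further detail.

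For analysis, SAP 3.3.4 gives the substudy one sentence: its data "will be summarized in separate tables using the same approach as for the main study if the data is ready by the primary analysis". For the main study, the same section says that descriptive statistics and "changes from baseline values at each time point will be provided". It also states, without condition, that all ECG data will be listed.

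Baseline is set twice. SAP 2.1 has: "Unless stated otherwise, baseline is defined as the last non-missing value prior to the first dose of study drug administration". SAP 3.3, which covers all safety summaries, repeats it with no exception: "Baseline is defined as the last non-missing value prior to the first dose of study drug administration". SAP 2.1 adds that descriptive statistics "will be summarized by treatment group for continuous variables". SAP 3.2 confines hypothesis testing to the co-primary and key secondary efficacy endpoints.

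**The concern.** The extraction schedule and the analysis rule do not match. The vendor is asked for replicates at three predose timepoints, and the summary rule uses the last of them. The SAP also does not say how replicates within a timepoint are combined, so a programmer could take the -15 minute average or a single tracing.

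The second gap is the comparison. The trial has a concurrent 1:1 placebo arm, but the planned output is change within each arm. Baseline is taken during ongoing status epilepticus, and both arms receive standard of care, so a within-arm change can mix any drug effect with a changing clinical state. A between-arm difference with an interval would address that from data already collected.

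At stake is the precision and usefulness of the trial's most detailed QT data. Protocol Table 1 (footnote g) schedules the safety ECG at predose, 2 hours, IP discontinuation, 24 hours after discontinuation and hospital discharge. The other PK-matched times have no scheduled ECG outside the substudy.

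**Working it through.** The documents give no figure for the substudy (no sample size, SD, precision target or threshold), so there is none to reproduce. The check has two parts.

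**Which rule applies.** SAP 3.3.4 sends the substudy to the main-study approach. SAP 3.3 and 2.1 make that the last predose value, summarised by arm. SAP 2.1 allows exceptions, and the SAP makes one elsewhere: baseline seizure burden (SAP 3.2.3.5) is defined over the 30 minutes before dosing. None is made for ECG. So one of three predose timepoints is used, and no section plans a between-arm QTcF estimate.

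**What averaging could gain.** Treat each timepoint as one value, with replicates already combined. Let

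- s = within-participant SD at a timepoint, in ms (assumed);
- m = number of predose timepoints averaged: 1 under the SAP, 3 if all are used (Appendix 5);
- r = correlation among the predose errors (assumed), with post-dose error independent of them. A participant's stable level cancels from the change, so s and r describe what remains.

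SD of change = s × √(1 + (1 + (m − 1)r)/m).

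With m = 1 this is s√2 = 1.414s, whatever r is. With m = 3 and r = 0 it is s√(1 + 1/3) = 1.155s. The SD ratio is 1.155/1.414 = 0.816 (18% lower); the variance ratio is 1.333/2 = 0.667 (33% lower).

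| r | Variance ratio, mean of 3 vs last value | SD ratio | SD reduction |
|---|---|---|---|
| 0 | 0.667 | 0.816 | 18% |
| 0.25 | 0.750 | 0.866 | 13% |
| 0.5 | 0.833 | 0.913 | 9% |
| 0.75 | 0.917 | 0.957 | 4% |
| 0.9 | 0.967 | 0.983 | 2% |

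**On the millisecond scale.** The 90% half-width for a between-arm difference in change is 1.645 × SD × √(2/n), with n per arm assumed. For s = 8 and n = 20:

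- last value: 1.645 × 11.31 × 0.316 = 5.9 ms;
- mean of three, r = 0: 1.645 × 9.24 × 0.316 = 4.8 ms;
- mean of three, r = 0.5: 1.645 × 10.33 × 0.316 = 5.4 ms.

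With s = 8, at n = 10 the three figures are 8.3, 6.8 and 7.6 ms; at n = 40 they are 4.2, 3.4 and 3.8 ms. Across s = 5 to 12 ms and n = 10 to 40, the last-value half-width runs from 2.6 to 12.5 ms, and the three-timepoint mean at r = 0 from 2.1 to 10.2 ms.

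These are unadjusted changes. True between-person variation in change would make the proportional gain smaller, and the gain under baseline adjustment is not computed here. If the last value were a single tracing rather than a replicate mean, the loss would be larger, by an amount that the documents do not allow one to size.

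**The case against.** The best opposing case is that this is a descriptive safety substudy. The documents set no QT objective, threshold or precision target, and descriptive by-arm tables are how the SAP treats all safety data. Placebo appears beside ganaxolone, so means can be subtracted. The Cardiodynamic ECG Manual, not among the documents, may define baseline or replicate handling. Appendix 5 gives no purpose for the three timepoints. Eligibility requires seizure activity in the 30 minutes before dosing, so the predose state may be moving, and the -15 minute value may be nearer the state at dosing than a mean reaching back to -45 minutes.

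Much of this stands. It limits the point to precision and reporting, makes 18% an upper bound, and argues for keeping the last value as a sensitivity summary. It does not remove the gap: subtracting two means gives no interval, and the SAP does not defer to the manual for the analysis.

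Three stronger readings are tempting but unsupported:

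- A reader might infer that the readiness clause permits no report at all. It conditions only the summary tables, and ECG listings are unconditional.
- A reader might infer that the two earlier predose timepoints are lost. They are unused as baseline, but remain in the listings.
- A reader might link this to the QTcF example among the withdrawal criteria (Protocol 4.5.2). That concerns one participant's 12-lead ECG, confirmed by a repeat tracing; the summary method for the substudy does not touch it.

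Nor do the documents say that QT shifts in both arms as seizures stop. That is plausible, but an assumption.

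**Conclusion.** The point holds as a minor, cheap improvement. Under the text as written, the substudy baseline is the last predose value, replicate handling is unspecified, no between-arm QTcF difference or interval is planned, and tables that miss the primary analysis have no stated destination. Those four statements rest on the documents alone.

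The size of the noise does not. Averaging would reduce the SD of change by at most 18%, with independent predose errors; readings 15 minutes apart in one patient may well be correlated, and the gain falls to 9% at r = 0.5 and 2% at r = 0.9. The missing contrast and the undefined replicate handling matter whatever r is. Efficacy conclusions are not affected.

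**What to change.** In SAP 3.3.4, for the substudy only:

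- average the replicate ECGs within each timepoint;
- define baseline as the mean over the -45, -30 and -15 minute timepoints, with the last-value baseline kept as a sensitivity summary;
- report the baseline-adjusted ganaxolone-minus-placebo difference in QTcF change at each PK-matched timepoint with a two-sided confidence interval, descriptively and without formal testing. A 90% level would serve, but that is a choice, since the documents set none;
- state that substudy tables not ready by the primary analysis will be reported in the clinical study report or an addendum.

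If the Cardiodynamic ECG Manual already defines baseline or replicate handling, the SAP should cite it and agree with it.

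The cost is a short SAP edit and some reprogramming of the substudy tables. No new ECGs are needed, and no dosing or clinical rule changes.
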